**Table 2: Analysis Sets**

Analysis Set	Description
FAS	All randomized participants who received at least 1 dose of the study drug (ravulizumab or placebo) in RCP. The primary population for efficacy assessment is the FAS. Participants will be compared for efficacy according to the treatment they were randomized to, regardless of the treatment received.
PKAS	All participants who receive at least 1 dose of the study drug and have at least 1 postdose PK sample
PDAS	All participants who receive at least 1 dose of the study drug and have at least 1 postdose PD sample
OLES	All participants who received at least 1 dose of ravulizumab starting from Week 50

Abbreviations: FAS = Full Analysis Set; OLE = Open-Label Extension; OLES = Open-Label Extension Set; PD = pharmacodynamic; PDAS = Pharmacodynamic Analysis Set; PK = pharmacokinetic; PKAS = pharmacokinetic analysis set; RCP = Randomized Controlled Period; SS = Safety Set

If the Randomized Set is identical to the Full Analysis Set (FAS), then the FAS will be used for disposition, demographics, and baseline characteristics.

## 5. STATISTICAL ANALYSES

### 5.1. General Considerations

All data collected in this study will be presented using summary tables, figures, and data listings.

- For the RCP, data summaries and inferential analyses will be presented by the treatment arms (“Ravulizumab” and “Placebo”). For certain noninferential summaries (demographics, baseline characteristics, and other prestudy information, including medical and ALS history, prior medications, and SAEs captured between screening and first infusion), a “Total” group may be formed by combining participants from both treatment arms. No “Total” group will be formed for efficacy and safety-related summaries.
- For the OLE Period, data summaries will be presented by the treatment arms (“Ravulizumab/Ravulizumab” and “Placebo/Ravulizumab”). A “Total” group may be formed by combining participants from both treatment arms.

Statistical analyses will include tabulations of summary data, inferential analyses, by-patient listings, and figures. The summary statistics for continuous variables will include, but not be limited to, the number of participants, mean, SD, minimum, median, and maximum. For categorical variables, frequencies and percentages will be presented. Inference from efficacy analyses will be based on a 2-sided Type I error ( $\alpha$ ) = 5% unless stated otherwise. The 95% confidence intervals (CI) will be produced where applicable. All p-values and CIs will be used for descriptive purposes only due to the study meeting the futility criterion.

Since the study has stopped for futility, multiplicity adjustment will not be considered.

The baseline value for analysis and reporting will be based on the last non-missing measurement on or prior to the first dose of the study drug unless stated otherwise.

Missing safety data will not be imputed.

Analyses will be performed using the SAS® software Version 9.4 or higher. Adverse events (AEs) will be coded with Medical Dictionary for Regulatory Activities (MedDRA) Version 24.0 or later. Prior and concomitant medications will be coded with World Health Organization (WHO) Drug Dictionary Version 202103 or later.

## 5.2. Study Participants

[figure not shown]
The following information will be summarized:

- The number and percentage of participants for the categories provided below (Figure 2 provides a flowchart related to the disposition)
  - Screened
  - Screen failure reasons (including coronavirus disease [COVID]-19 related screen failures)
  - Randomized
  - Treated
  - Included in the interim analysis 1
  - Completed RCP
  - Discontinuation reasons (RCP)
  - Did not roll over to OLE
  - Treated in OLE
  - Discontinuation reasons (OLE)
  - Completed OLE/study
- The number and percentage of participants randomized to placebo or ravulizumab within each of the 6 stratification levels (Table 1); the percentages will be calculated based on the total number of participants within each stratification level
  - By planned randomization strata (derived strata based on the bulbar onset and stable riluzole or edaravone use)
  - By actual randomization strata (observed stratification)
- A cross-tabulation of participants by planned and actual randomization strata for quantifying the mis-stratification
- The number and percentage of participants by protocol scheduled visits during RCP
- The number and percentage of participants in analysis datasets and reason for exclusion from specific datasets
- The number and percentage of participants who missed a study visit along with associated reasons including reasons related to COVID-19
- The number and percentage of participants who had a delayed visit along with associated reasons including reasons related to COVID-19

- The number and percentage of participants with a visit modification along with associated reasons including reasons related to COVID-19

Details will be presented in the listings.

**Figure 2: Participant Disposition Flowchart**

### 5.3. Primary Estimand and Analysis

The primary endpoint for this study is based on ALSFRS-R. It is a validated instrument for evaluating the levels of the physical functional status of patients with ALS in 4 areas, including bulbar, gross motor activity, fine motor activity, and respiratory functions. The scale includes 12 functional items, and each item is rated on a 0 to 4 scale, with a maximum total score of 48. A higher score indicates greater retention of function. The ALSFRS-R assessment schedule is provided in the Schedule of Activities in the protocol. If a participant is unable to attend the scheduled onsite visit, the ALSFRS-R can be assessed via a phone call by the Investigator or trained designee.

A joint rank analysis (referred to as CAFS) recommended in the [Food and Drug Administration \(FDA\) guidance document on ALS, 2019](#), which combines deaths and ALSFRS-R, will be performed for the analysis of the primary endpoint. This analysis will be conducted based on the FAS.

#### 5.3.1. Estimand

The 5 attributes for the primary estimand are described below:

- Treatment: ravulizumab or placebo with or without the use of stable riluzole and edaravone
- Population: adult participants with ALS as defined by the protocol inclusion/exclusion criteria

- Variable: CAFS score (defined below) based on the monthly slope in ALSFRS-R (change from Baseline in ALSFRS-R total score at last visit on or before Week 50 divided by the corresponding time [month]) and time (months) to death during RCP
- ICE: death
  - The composite strategy will be adopted to account for death in analysis for the primary endpoint (see Section 5.3.2 for details)
- Population-level summary: mean CAFS score (defined below)
  - The treatment effect will be quantified by the difference in mean between ravulizumab and the placebo arms

For participants who do not survive until Week 50, ALSFRS-R total scores will be missing, which may bias the evaluation of clinical benefit if not adequately accounted. This joint rank analysis evaluates function while accounting for missing data due to deaths in ALS by calculating a CAFS score for each participant.

**CAFS scoring:** For calculating the CAFS score, each participant will be compared individually to all other participants (irrespective of treatment assignment) in a pairwise fashion (Berry, 2013). For each pairwise comparison, the participant who fares better earns a point (+1), and the participant who fares worse loses a point (-1). In the case of a tie, no points (0) are added or subtracted. Each participant's summary score (CAFS score) is the sum of the comparisons (+1, 0, -1) against all other participants.

1. If both participants die, the participant surviving longer will earn a point (+1) and the participant with a shorter survival time will lose a point (-1); no points (0) are added or subtracted if the survival times are identical.
2. If only 1 participant survives, then that participant will earn a point (+1)
3. If both participants survive, the participant with the smaller decline in the slope of ALSFRS-R will earn a point (+1), the participant with the larger decline will lose a point (-1), and no points (0) are added or subtracted in the case of a tie. The slope will be calculated based on the change from Baseline in ALSFRS-R total score at the last available visit normalized by the number of months between the first study drug and the last available visit. For a participant that discontinued early without any information on death or change in ALSFRS-R, the slope will be assumed zero as it is unlikely that the ALSFRS-R score will change significantly within a short period.

Participants will be ranked based on the CAFS score, as calculated above, irrespective of the treatment assignment. The first participant who dies will have the lowest score and is ranked the lowest; the last to die is ranked above all others who die; among survivors, the participant with the greatest decline in ALSFRS-R slope is ranked immediately above the last participant who died; the surviving participant with the least decline in ALSFRS-R slope is assigned the highest rank. Participants with the same CAFS scores will be ranked with average ranks.

Section 6.2.3 provides examples of CAFS scoring.

### 5.3.2. Main Analytical Approach

The analysis of CAFS ranks will be based on an analysis of covariance model. The model will include the CAFS ranks as the dependent variable and the following list of independent variables: treatment indicator (0 = placebo, 1 = ravulizumab), age, sex, baseline ALSFRS-R total score, baseline SVC percent predicted, months since first muscle weakness onset at Baseline, and the stratification factors.

If the 2-sided p-value associated with the higher mean rank in the ravulizumab group compared to the placebo is less than  $\alpha = 0.05$ , a statistically significant treatment benefit will be established. The least squares (LS)-means and the 95% CIs of the CAFS ranks for each treatment arm and the difference between the arms will be calculated. Details will be provided in a listing.

This analysis will be conducted for sake of completion and will not support efficacy conclusion as the study met the pre-specified futility criteria.

### 5.3.3. Sensitivity Analysis

The following sensitivity analysis will be conducted to quantify the treatment effect magnitude.

#### 5.3.3.1. Sensitivity Analysis: Mixed-effect Model for Repeated Measures

As the CAFS method is based on ranks and cannot quantify the magnitude of the treatment effect for ALSFRS-R, a sensitivity analysis will be performed, including all ALSFRS-R longitudinal data (either complete or partial), to estimate the treatment effect, ie, the difference in mean change from Baseline between ravulizumab and placebo.

##### 5.3.3.1.1. Estimand

The 5 attributes for the estimand are described below:

- Treatment: ravulizumab or placebo with or without the use of stable riluzole and edaravone
- Population: adult participants with ALS as defined by the protocol inclusion/exclusion criteria
- Variable: change from Baseline in ALSFRS-R total score at the postbaseline visits during RCP up to and including Week 50.
- ICE: none
  - The treatment policy will be adopted, and all ALSFRS-R data will be used; no imputation will be performed for missing data due to death or discontinuation
- Population-level summary: mean change from Baseline in ALSFRS-R total score
  - The treatment effect will be quantified by the difference in mean between ravulizumab and the placebo arms.

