##### **9.4.5.1.1.1. Alternate Primary Analysis**

Per Committee for Medicinal Products for Human Use recommendation, an MMRM (mixed-effects model repeated measures) based analysis of the primary endpoint will be conducted for EMA submission. For this analysis, the missing ALSFRS-R scores due to deaths will be imputed as zero (worst score imputation) and other missing data will be imputed according to placebo-based mean trajectories. The model will include the change from baseline in ALSFRS-R total score at each nominal visit as the dependent variable and the following list of independent variables as fixed effects: actual time on study (months), the interaction between time and treatment (0 = placebo, 1 = ravulizumab), age, sex, baseline ALSFRS-R total score, baseline SVC, time from muscle weakness onset, and the stratification factors. In addition, the patient-specific random slope will be added to the model with an unstructured variance-covariance matrix to model the correlations among repeated measurements within each patient. Other covariance structures will be implemented if a convergence issue occurs (details to be provided in SAP). The Kenward-Rogers method will be used to estimate the denominator degrees of freedom. A p-value less than the Type I error = 0.05 associated with the higher mean change in ALSFRS-R total score in the ravulizumab group compared to placebo will indicate a statistically significant treatment benefit.

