##### 5.3.3.1.2. Analytical Details for Sensitivity Analysis

The model will include the change from Baseline in ALSFRS-R total score at each study visit as the dependent variable and the following list of independent variables as fixed effects: actual time on the study (months), the interaction between time and treatment (0 = placebo, 1 = ravulizumab), age, sex, baseline ALSFRS-R total score, baseline SVC percent predicted,

months since first muscle weakness onset at Baseline, and the stratification factors. The participant-specific random slope will also be added to the model with an unstructured variance-covariance matrix to model the correlations among repeated measurements within each participant. The following covariance structures will be implemented if a convergence issue occurs in the specified order:

- Heterogeneous toeplitz (TOEPH)
- Heterogeneous autoregressive (1) (ARH (1))
- Heterogeneous compound symmetry (CSH)
- Toeplitz structure (TOEP)
- Autoregressive (1) (AR (1))
- Compound symmetry (CS)

The first covariance structure that converges will be used. The Kenward-Rogers method will be used to estimate the denominator degrees of freedom.

No imputation for the missing data will be performed after discontinuation (death or dropout) from the study, assuming the data are missing at random (MAR).

Section 6.2.9 provides details on implementing analysis windows.

A 2-sided p-value less than  $\alpha = 0.05$  associated with the higher mean change in ALSFRS-R total score in the ravulizumab group compared to placebo will indicate a statistically significant treatment benefit. The LS-means and the 95% CIs of the mean change from Baseline at Week 50 for each treatment arm and the difference between the arms will be calculated. The treatment effect will be evaluated via the estimated treatment-by-visit interaction term at Week 50 (Month 11.5). Details will be provided in a listing.

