#### **5.4.1.2. Slow Vital Capacity Percent Predicted**

##### **5.4.1.2.1. Estimand**

The 5 attributes for the estimand related to SVC percent predicted are described as follows:

- Treatment: ravulizumab or placebo with or without the use of stable riluzole and edaravonee
- Population: adult participants with ALS as defined by the protocol inclusion/exclusion criteria and included in the FAS
- Variable: change from Baseline in SVC percent predicted at Week 50 based on the in-clinic assessment or the at-home assessment when in-clinic assessment is not available
- ICE: none. The treatment-policy strategy will be adopted.
- Population-level summary: mean change from Baseline in SVC percent predicted at Week 50; the treatment effect will be quantified by the difference in mean between ravulizumab and the placebo arms.

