##### **5.4.1.2.2. Main Analytical Approach**

The treatment effect on SVC percent predicted will be evaluated based on a mixed-effect model repeated measure with the change from Baseline in SVC percent predicted as the dependent variable and the following list of independent variables as fixed effects: actual time on study (months), time and treatment interaction, age, sex, baseline ALSFRS-R total score, baseline SVC, disease duration, and the stratification factor. In addition, the participant-specific random slope will be added to the model with an unstructured variance-covariance matrix. The strategy for selecting other covariance structures outlined in Section 5.3.3.1.2 will be used if a convergence issue occurs. The Kenward-Rogers method will be used to estimate the denominator degrees of freedom. No imputation for the missing data will be performed after death or discontinuation, assuming the data are MAR.

A 2-sided p-value less than  $\alpha = 0.05$  associated with the higher mean change in SVC percent predicted in the ravulizumab group compared to placebo will indicate a statistically significant treatment benefit. The LS-means and the 95% CIs of the mean change from Baseline at Week 50

(month 11.5) for each treatment arm and the difference between the arms will be calculated. Details will be provided in a listing.

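### The ALSFRS-R mixed model and the key-secondary SVC model are labelled treatment policy with no intercurrent event, yet they put death under missing at random and so estimate outcomes as if patients had not died

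*SAP*

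**What the plan says.** **ALSFRS-R mixed model.** SAP 5.3.3.1.1 lists no intercurrent event and adopts treatment policy, adding that "no imputation will be performed for missing data due to death or discontinuation". SAP 5.3.3.1.2 places both death and dropout under MAR. Table 3 repeats the entry: no intercurrent event, treatment policy.

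**SVC percent predicted, a key secondary.** The objectives table in SAP 1.1 gives treatment policy. SAP 5.4.1.2.1 reads "ICE: none. The treatment-policy strategy will be adopted". SAP 5.4.1.2.2 then says: "No imputation for the missing data will be performed after death or discontinuation, assuming the data are MAR".

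**Primary analysis on the same scale.** SAP 5.3.1 names death as the intercurrent event: "The composite strategy will be adopted to account for death in analysis for the primary endpoint". It explains that for patients who die before Week 50, "ALSFRS-R total scores will be missing, which may bias the evaluation of clinical benefit if not adequately accounted".

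**What was there before.** Protocol 9.4.5.1.1.1 defined a mixed-model analysis that scores ALSFRS-R after death as zero and fills other gaps from the placebo arm's mean course. Protocol 9.4.5.1.2.2, which leaves deaths unimputed, points the reader to it. SAP Appendix 4 records that version 2 deleted the alternate primary analysis, all but one of the ALSFRS-R sensitivity analyses and the SVC sensitivity analysis. SAP 5.3.3.1 gives the remaining mixed model the job of stating the size of the effect, because ranks cannot.

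**The concern.** Treatment policy means using the value that occurs whether or not the event happens. After death there is no such value, so the strategy is undefined for that event. What the model does instead is fixed by its form. With a patient-specific slope and a time-by-treatment term read off at Month 11.5, a MAR likelihood predicts the unobserved visits of a patient who died from the slope seen before death. The result is the mean expected had nobody died.

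One SAP thus treats death as an intercurrent event for ALSFRS-R in the primary analysis and as no event in the analysis meant to give the magnitude. At stake is what a reader takes from two reported numbers. Labelled as they are, they would be read as effects in all randomised and treated patients regardless of events, while a survival benefit or harm leaves almost no trace in them.

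**Working it through.** **Inputs from SAP section 3.** Placebo slope 1.19 points per month; 30% slope reduction; SD 10.3; 2:1 allocation of 354 (118 placebo, 236 ravulizumab); 82% one-year placebo survival; mortality hazard ratio 0.5. SAP 5.3.3.1.2 equates Week 50 with Month 11.5.

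**Assumption not in the documents.** Baseline ALSFRS-R of 38 (range 36 to 40).

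**1. Reproducing the plan's own figure.** The difference is 14.3 − 10 = 4.3. By the normal approximation, placebo n = 1.5 × (1.96 + 1.2816)² × (10.3/4.3)² = 90.4, so 91 and a total of 273. A two-sided t-test at 2:1 needs 276, and at 282 (94 and 188) its power is 90.9%. Dropout: 282/0.8 = 352.5, so 353, or 354 as a multiple of 3. The plan's at-least-90% statement holds.

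**2. Expected deaths by Week 50 (Day 350).**
- Placebo: 1 − 0.82^(350/365.25) = 17.3%, or 20.4 of 118.
- Ravulizumab: 1 − 0.82^(0.5 × 350/365.25) = 9.1%, or 21.4 of 236.
- Total: about 42 of 354 (12%).

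**3. The MAR slope model.** Placebo −1.19 × 11.5 = −13.69; ravulizumab −0.833 × 11.5 = −9.58; difference 4.1. With no effect on slope, the difference is 0 whatever the mortality.

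**4. Death scored as zero, if death is unrelated to rate of decline.**
- Ravulizumab: 0.909 × (−9.58) + 0.091 × (−38) = −12.16.
- Placebo: 0.827 × (−13.69) + 0.173 × (−38) = −17.90.
- Difference: 5.74 (5.6 at baseline 36, 5.9 at baseline 40).
- Survival-only effect: (0.1732 − 0.0907) × (38 − 13.69) = 2.0.

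**5. Letting death depend on decline.** Faster decliners probably die sooner, so this was simulated: 400 trials per scenario, baseline 38, residual SD 2, slope SD √(10.3² − 2²)/12 = 0.84 per month, and no dropout other than death. The log hazard of death per SD of faster decline was set to 0, 0.5 or 1. All but the mortality and slope inputs are assumptions. Results are ravulizumab minus placebo, in points, at Month 11.5.

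| Scenario | Method | Link 0 | Link 0.5 | Link 1 |
|---|---|---|---|---|
| 30% slope benefit, HR 0.5 | MAR slope | 4.1 | 4.1 | 3.9 |
| | Death = 0 | 5.7 | 5.5 | 5.1 |
| No slope effect, HR 0.5 | MAR slope | −0.1 | −0.1 | −0.2 |
| | Death = 0 | 2.0 | 1.7 | 1.4 |
| No slope effect, HR 2 | MAR slope | −0.1 | 0.2 | 0.5 |
| | Death = 0 | −3.5 | −2.9 | −2.2 |

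The zero-for-death figures in steps 4 and 5 are differences between arm means at Week 50, not fits of the protocol's random-slope model. No comparable figure can be given for SVC, because the documents state no SVC planning values.

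**The case against.** The strongest case against has four parts.

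- **Death is not ignored by the plan.** It is the intercurrent event of the primary CAFS analysis and a component of VAFS. SAP 5.4.1.1.3 gives time to death its own Cox model, Kaplan-Meier curves and a summary by reason. This stands. A reader might infer that a survival benefit or harm would be hidden from the report, or that no effect estimate accounts for death. The documents do not support that. The gap is confined to the effect in ALSFRS-R points and the effect on SVC.
- **The bias warning is conditional and narrow.** It concerns ALSFRS-R and introduces CAFS as the remedy. This also stands, so it would be wrong to say that the SAP warns about its own SVC model. Extending the reasoning to SVC is inference, though a reasonable one: Protocol 3.2.3.2 says SVC correlates with ventilation and death.
- **The missing-data rule is open.** Both models say in words that death falls under MAR. True, but this tells the reader what is done with the data and leaves the wrong name on what is estimated.
- **Futility has been declared.** SAP 5.1 makes all p-values and intervals descriptive, and Appendix 4 records why analyses were dropped. So type I error and the efficacy decision are not at issue, and the deletions were not improper. A descriptive estimate still needs a correct label.

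**Conclusion.** The estimand labels are wrong as written for both models. Each estimates a mean as if patients had not died, which is a hypothetical strategy. Under the planning assumptions the choice matters by roughly 1 to 1.6 points on ALSFRS-R: 5.1 − 3.9 = 1.2 with the strongest link between death and decline examined, and 5.7 − 4.1 = 1.6 with none. A survival-only benefit gives 1.4 to 2.0 points with death scored as zero and about 0 under MAR. Doubled mortality gives −3.5 to −2.2 against −0.1 to +0.5.

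A reader might take the narrower 5.6 to 5.9 as the plausible range. It varies only the baseline and holds only if death is independent of decline. All the figures use design-stage effects for a trial already stopped for futility, so they show how the two definitions differ and do not predict what this SAP will report. The point concerns interpretation of descriptive estimates and calls for a correction of modest size.

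**What to change.** 1. In the SAP 1.1 objectives table (SVC row), 5.3.3.1.1, Table 3 and 5.4.1.2.1, list death as an intercurrent event handled by a hypothetical strategy for these two models. State that the estimates describe function as if patients had not died.
2. Beside the ALSFRS-R mixed model, report the zero-for-death analysis already defined in Protocol 9.4.5.1.1.1, marked as descriptive only.
3. For SVC, relabel and refer the reader to the VAFS and mortality results in 5.4.1.1. A joint-rank SVC analysis is optional: neither current document defines one, and it would be devised after the futility result.

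The cost is four text edits and one added analysis on existing data. That analysis is a little more than a rerun, because its placebo-based imputation of other missing scores must be specified again; Appendix 4 shows that the appendix of additional statistical methods was also deleted.
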